## Background & Significance

To reduce the rising cost of cardiac operations, researchers have studied early extubation as a means to shorten ICU length of stay, and favorably influence patients' health outcomes. In the process, various nursing ICU protocols have been developed to facilitate the expedient tracheal extubation of patients, taking into account hemodynamic status, mediastinal drainage, urine output, patient temperature (rewarming from induced hypothermia), and other factors.

Hypothermia on admission to the ICU following CPB is common. Cooling and rewarming during CPB and takes considerable time and contributes to the post-procedural coagulopathy and physiologic perturbations.

Rewarming in the postoperative period after hypothermic CPB is often associated with hemodynamic and ventilatory instability. Temperature changes, PaCO2 values, and mechanical ventilation were observed for the first 12 hours in the ICU in 73 patients who had undergone cardiac surgery with hypothermic CPB. Mean rectal temperature increased from 34.7 to 38.3 degrees C over the first 8 hr after admission to the ICU. The temperature curve was sigmoid rather than linear, and the most rapid rate of temperature increase occurred 2-4 hours after admission. During rewarming, the most common abnormality of PaCO2 on mechanical ventilation was acute respiratory acidosis (PaCO2 greater than 45 mmHg, pH less than 7.35), which occurred in 42% of patients.

After disconnecting from CPB the body is allowed to self-equilibrate. The normal vasoconstriction response is impaired by the administered anaesthesia. Hence, heat distribution takes place from the warm core to the colder periphery. This causes an afterdrop: a decrease in the temperature of the core organs. After-drop may contribute to post-operative complications of hypothermia such as shivering, coagulopathy, increased myocardial stress, increased wound infections, metabolic acidosis, delayed extubation and prolonged ICU length of stay.

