## **Design & Procedures**

Hypothermia ( $\leq 35$  °C) after cardiac surgery using CPB is not uncommon. To avoid complications associated with hypothermia, and due to absence of shivering when patient is sedated, and harmful effects of shivering when patient is awake, clinicians resort to active warming devices. Forced air warming devices are the most commonly utilized, but occasionally heated humidified breathing circuits are used as well. We plan to use both warming devices on study patients, and compare them with a historical cohort that has used forced air warming device only.

On admission to CTICU, if temperature  $\leq 35$  °C, we will attempt to recruit the patient. Patients are intubated and sedated on admission to the CTICU after cardiac surgery, so informed consent will be obtained from the patient's next of kin or power of attorney. After consent is obtained, the clinical provider will ask the patient's nurse to place a lower body forced air warming device and set to 38 °C, and ask the respiratory therapist to set up and connect a heated humidified breathing circuit.

Admission temperature and other vital signs will be recorded per CTICU standards. Other patient management decisions (ie medication changes, laboratory assessments...etc) per direction of ICU providers. Core temperature and location (esophageal, nasopharyngeal, bladder, rectal, blood) will be recorded every 15-30 minutes until normothermia reached (36.5 °C), then record per CTICU standard. Record active warming methods in nursing flow sheets (i.e. Forced air warming blanket and heated humidified breathing circuit). Record other vital signs, medications, extubation time, hourly chest tube output, and patient data per unit policy. Alert Respiratory therapy once normothermia (36.5 °C) has been achieved for discontinuation of HHBC.

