#### **Risk/Benefit Assessment**

Heated humidified breathing circuits are being used clinically to avoid / treat hypothermia both in the OR and the ICU. We aim to examine if this clinical practice provides additional benefit to the forced warm air devices. Risks associated with heated humidified breathing air includes: possible inefficient warming of body temperatures, thermal injury to airways, excessive heating (hyperthermia).

There is also a potential risk of loss of confidentiality. Every effort will be made to keep your information confidential, but this cannot be guaranteed. Those risks can be minimized by frequent monitoring and documentation of both the device temperature as well as the patient temperature every 15-30 minutes to avoid over heating, and make sure active rewarming is stopped when temperature of patient exceeds 36 C.

If patient's power of attorney declined to participate in the study, only forced air warming will be used for active rewarming of patient.

Possible benefit if using warm humidified air is more effective in rewarming patients when combined with forced warm air devices than when using forced warm air devices alone, hypothermia will resolve quicker, potentially minimizing complications associated with hypothermia such as coagulopathy, shivering, metabolic derangements, etc.

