### **Data Analysis & Statistical Considerations**

Descriptive statistics will be used to evaluate patient demographics and clinical characteristics. Descriptive statistics will be summarized as mean  $\pm$  (SD) or median (interquartile range) for continuous variables and group frequencies (%) for dichotomous or categorical variables.

As all patients are expected to achieve normothermia within the study period, the primary outcome of time to normothermia will be analyzed as a numeric outcome variable. Following validation of distributional assumptions we will compare the time to normothermia between the two groups via t-test or Wilcoxon rank sum test as appropriate. It is expected that the patients will reach normothermia between 45 minutes and 6 hours after admission to the ICU.

By using a 2:1 matching ratio and a moderate level of variability (SD=1.3 hours) a study of 14 prospectively enrolled patients and 28 retrospectively matched patients would attain 82% power to detect a 1.25 hour difference between time to normothermia in the two groups at alpha level 0.05.

Secondary numeric outcomes such as time to extubation, time to normal PH, and coagulopathy lab values will be analyzed by t-test or Wilcoxon rank sum test as appropriate. Differences in categorical outcomes between treatment groups such as shivering will be analyzed via chi-square or fisher exact tests. As the patients will be matched on key confounders no further adjustment is expected to be necessary, so the moderate sample size should not limit the primary analysis. Potential subgroup analysis may be conducted in an exploratory analysis to determine if the treatment effect of ANAPOD warming is different by procedure type or patient/surgical characteristics.

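### Time to normothermia may be read at different intervals in the two groups, and the plan gives no common rule for deriving it, so a first-reading derivation would bias the primary comparison by half the difference in intervals

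*Combined protocol and SAP*

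**What the plan says.** Design & Procedures sets a schedule for enrolled patients: core temperature "will be recorded every 15-30 minutes until normothermia reached (36.5 °C), then record per CTICU standard". That schedule is distinct from unit routine, which governs the rest: "Admission temperature and other vital signs will be recorded per CTICU standards". Risk/Benefit Assessment repeats the interval as a safeguard against overheating, calling for "frequent monitoring and documentation of both the device temperature as well as the patient temperature every 15-30 minutes"; it does not give the 36.5 °C limit.

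The comparator is retrospective. Design & Procedures says the investigators will "compare them with a historical cohort that has used forced air warming device only". No section gives the interval at which those patients' temperatures were charted. Reading frequency is not among the matching criteria listed for the retrospective part.

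In Data Analysis & Statistical Considerations, "the primary outcome of time to normothermia will be analyzed as a numeric outcome variable", and the plan is to "compare the time to normothermia between the two groups via t-test or Wilcoxon rank sum test as appropriate". The section expects no adjustment beyond the matching. Nowhere is it stated how a time is obtained from readings taken at intervals.

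**The concern.** Temperature is seen only when it is read. A patient who crosses 36.5 °C between two readings is recorded as crossing at the later one if the first qualifying reading is used. That is the natural derivation when a plan is silent. The average delay is half the reading interval. If both groups share an interval, the delays cancel. If they do not, the difference in delays enters the estimated treatment effect as a fixed shift.

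Neither planned test can separate that shift from a real effect, and matching on patient characteristics does not touch it, because it comes from how the outcome is measured. Leaving the derivation open until the control charts have been seen also adds analyst discretion to a non-randomised comparison of 42 patients.

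**Working it through.** **Inputs from the plan.** 14 HHBC patients and 28 controls; SD 1.3 h; target difference 1.25 h; alpha 0.05; HHBC interval 15-30 min; normothermia expected between 0.75 and 6 h.

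**Assumptions.** Control charting interval, shown as a range with no case preferred; readings at random phase relative to the true crossing; mean time 3.375 h, the midpoint of 0.75 and 6 h; two-sided test.

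**The plan's own figure.** Standard error = 1.3 × √(1/14 + 1/28) = 0.4255 h. The two-sided t-test with 40 degrees of freedom has 81.8% power for 1.25 h, which reproduces the stated 82%. The smallest significant observed difference at this SD is 2.021 × 0.4255 = 0.86 h.

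**Bias under a first-reading rule.** Expected delay = interval/2 in each group, so

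bias = (control interval − HHBC interval)/2, positive values favouring HHBC.

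Hourly controls: (1 − 0.25)/2 = 0.375 h, or (1 − 0.5)/2 = 0.25 h. As shares of the target, 0.375/1.25 = 30% and 0.25/1.25 = 20%.

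Type I error comes from 40,000 simulated null trials per cell. Each pair is for HHBC read every 15 / 30 min; the minute-level biases are rounded.

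| Controls charted (assumed) | Bias, h | t-test | Wilcoxon |
|---|---|---|---|
| every minute | −0.12 / −0.24 | 6.0% / 8.8% | 5.7% / 8.3% |
| every 15 min | 0 / −0.125 | 4.9% / 5.9% | 4.7% / 5.8% |
| every 30 min | +0.125 / 0 | 5.9% / 5.0% | 5.8% / 5.0% |
| hourly | +0.375 / +0.25 | 13.3% / 8.7% | 12.7% / 8.5% |

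Where the intervals are equal, type I error is about 5%. The inequality does the damage, not the coarseness.

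**Does interpolation alone cure it?** Linear interpolation between the last reading below and the first at or above 36.5 °C removes the half-interval delay. With noisy readings, though, the more densely read group has more chances of an early false crossing. Take a straight rise of (38.3 − 34.7)/8 = 0.45 °C/h, from Background & Significance ("Mean rectal temperature increased from 34.7 to 38.3 degrees C over the first 8 hr"), and hourly controls. The residual bias (HHBC every 15 / 30 min) is then:
- no noise: +0.004 / +0.002 h
- noise SD 0.1 °C (assumed): +0.036 / +0.009 h
- noise SD 0.2 °C (assumed): +0.171 / +0.062 h, type I error 6.9% / 5.4%

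**Thinning first, then interpolating.** On a common 60-minute interval, bias is within 0.006 h and type I error is 4.8-5.3% for noise of 0-0.2 °C. With irregular control charting (30, 60 and 120 min in 30%, 50% and 20%, assumed) and HHBC thinned to the 60-minute median, bias is within 0.021 h and type I error 5.0-5.1%. Power for 1.25 h on a common hourly interval is about 82% without noise, falling to about 79% at 0.2 °C.

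**The case against.** The strongest reply is that no bias has been shown. The plan gives neither a first-reading rule nor a control interval. If controls were charted every 15-30 minutes, the problem is negligible; if they were charted more often, the bias runs against HHBC. This stands, and it limits the claim to a conditional one. It does not remove the need for a rule, because the primary outcome cannot be computed without one.

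A reader might infer that the plan favours HHBC, since the study schedule is set apart from unit routine. The wording suggests that routine is sparser but does not establish it.

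A reader might also infer that ascertainment alone could produce a positive trial. With hourly charting, 0.25-0.375 h is well below the 0.86 h needed for significance. Only much sparser charting changes that: 2-hourly controls would give 0.75-0.875 h and t-test type I error of 37-47%. Nothing in the plan supports that interval.

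A third reply is that straight-line interpolation misfits a curve of which the plan itself says "The temperature curve was sigmoid rather than linear". In the cited series, however, 36.5 °C is the midpoint of the range, (34.7 + 38.3)/2, and warming was fastest at 2-4 hours, which contains the assumed mean crossing of 3.375 h. The curve is therefore close to straight where it matters. With a logistic curve over that range (slope constants 0.8-1.0 per hour, assumed), residual bias from interpolation alone at 0.2 °C noise and hourly controls is 0.01-0.07 h, smaller than on the straight line.

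**Conclusion.** The concern holds in conditional form. The plan sets a reading schedule for one group, inherits an unstated one for the other, and compares the resulting times with no common derivation rule. Under a first-reading rule the bias is half the difference in intervals: within ±0.125 h for controls charted every 15-30 minutes, and 0.25-0.375 h in favour of HHBC, with type I error of about 9-13%, for hourly charting. Size and direction remain unknown until the control charts are examined. The figures rest on the plan's SD of 1.3 h, random reading phase and the assumed control intervals. The point should be settled before control data are abstracted; it does not show that the trial's result would be wrong.

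**What to change.** In Data Analysis & Statistical Considerations, before control data are abstracted, state one derivation for both groups:

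1. Abstract the times and values of the control temperature readings up to 36.5 °C.
2. Thin the HHBC readings to the control charting interval, using the median if it varies, with the starting point of the thinned series fixed in advance. If controls prove to be the more densely charted group, thin theirs instead.
3. In both groups, take the crossing of 36.5 °C by linear interpolation between the last reading below it and the first reading at or above it.
4. Measure the time from one origin that exists in both groups. The retrospective selection criteria take ANAPOD application as the reference point, which controls do not have, while the analysis section counts from ICU admission. These must be reconciled.
5. Keep the planned t-test or Wilcoxon test.
6. Report the charting interval by group, and give the unthinned interpolated times as a sensitivity analysis.

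Thinning belongs in the primary analysis because it removes the residual bias that interpolation leaves when reading density differs. The cost is somewhat more chart abstraction and a small loss of power: about 79-82% for 1.25 h on a common hourly interval, for assumed reading noise of 0.2 °C down to none, against the planned 82%.

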## **Selection of Subjects**

For the prospective part of the study:

#### Inclusion Criteria:

Adult patients (18-85 years old) Admitted to CTICU following cardiac surgery using CPB.  
Admission temperature  $\leq 35.0$  °C.

#### Exclusion Criteria:

Patients admitted to ICU on ECMO support.

For the retrospective part of the study:

We will be matching the 14 prospective patients who received both ANAPOD and forced warm air with 28 retrospective ones who presented with hypothermia that were treated with forced warm air alone without ANAPOD. Criteria should include:

- Hypothermic Patients (Temp < 35C) undergoing cardiac surgery under CPB who received forced warm air alone.
- Temp at time of ANAPOD application would be our reference point.
- Type of surgery
- Patient's BMI
- Deep hypothermic arrest

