#### **Subject Recruitment and Compensation**

All adult patients (18-85 years old) Admitted to CTICU following cardiac surgery using CPB, with an admission temperature  $\leq 35.0$  °C will be considered for recruitment.

Both males and females and all demographic groups will be included.

Patients are intubated and sedated on admission to the CTICU after cardiac surgery, so informed consent will be obtained from the patient's next of kin or power of attorney by one of the patient's care providers or study personnel.

Approximately 14 patients will be included in the prospective recruitment of patients. Data will be matched with a historical cohort of 28 patients (2:1 matching).

No compensation will be offered.

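### The 28 historical controls are to be matched with no source window, tolerance, selection rule or outcome masking, so the unadjusted primary comparison is open to selection bias

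*Combined protocol and SAP*

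**What the plan says.** Design & Procedures says the study patients will receive both warming methods and that the investigators will "compare them with a historical cohort that has used forced air warming device only". The same section notes that in practice "occasionally heated humidified breathing circuits are used as well".

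The retrospective criteria, printed under Exclusion Criteria, call for "28 retrospective ones who presented with hypothermia that were treated with forced warm air alone without ANAPOD". Eligible controls are hypothermic patients "undergoing cardiac surgery under CPB who received forced warm air alone". The list then names type of surgery, BMI and deep hypothermic arrest, and adds that "Temp at time of ANAPOD application would be our reference point".

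Subject Recruitment and Compensation adds only "Data will be matched with a historical cohort of 28 patients (2:1 matching".

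Data Analysis & Statistical Considerations plans a t-test or Wilcoxon rank sum test on time to normothermia. It expects to need no adjustment because of the matching. It states that "14 prospectively enrolled patients and 28 retrospectively matched patients would attain 82% power" for a 1.25 hour difference at alpha 0.05, assuming "a moderate level of variability (SD=1.3 hours".

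None of these sections gives a calendar period, a source list, consecutive or random sampling, a tolerance for BMI or temperature, categories for surgery type, a rule for when more than two records fit, or masking of whoever makes the selection.

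**The concern.** In a historical-control study, the choice of controls does the work that randomisation would otherwise do. Here the control outcomes exist before the controls are chosen, and the criteria leave room for judgement. How close a BMI must be, which operations count as the same type, and which records to take if more than two qualify are all open. The temperature reference is tied to applying the heated circuit, an event that no control has, so where a control's baseline lies is also open.

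If time to normothermia can be seen while these choices are made, even a mild and unintended preference shifts the control mean. The planned test treats the 28 as if they had been drawn without regard to outcome and cannot detect or correct such a shift. Once outcomes have been seen during matching, this cannot be undone.

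A second, smaller question is how control status is defined. Because HHBC was sometimes used in routine care, the forced-air-alone condition can be read as removing past patients who began on forced air and were given HHBC afterwards. That would select controls on something that happened after rewarming began.

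**Working it through.** **Inputs.** From Data Analysis & Statistical Considerations: n = 14 and 28, SD 1.3 h, difference 1.25 h, alpha 0.05. Two-sided testing is inferred because it reproduces the stated power. The degree of preference and the number of eligible records are assumptions.

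**1. The plan's own figure.** SE = 1.3 × √(1/14 + 1/28) = 0.4255 h. Noncentrality = 1.25 / 0.4255 = 2.94 on 40 df; critical t = 2.021. Two-sided power = 81.8%, which agrees with the stated 82%. The sample-size arithmetic is sound. The smallest significant difference is 2.021 × 0.4255 = 0.86 h.

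**2. Sensitivity to a fixed shift in the control mean** (noncentral t, 40 df):

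| Assumed shift | Controls look slower, no true effect: chance of a significant result favouring HHBC (nominal 2.5%) | Controls look faster, true effect 1.25 h: power |
|---|---|---|
| 0.25 h | 8.3% | 63.1% |
| 0.50 h | 20.8% | 40.5% |
| 0.75 h | 40.5% | 20.9% |

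**3. What degree of preference would produce such shifts.** Simulation with no true effect, 14 treated patients, two controls each, normal times with SD 1.3 h and a pooled two-sided t-test. In a stated share of matched sets the slower two eligible records are taken; otherwise two are taken without regard to outcome.

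With four eligible records, the upper two of four standard normal values have expected values 0.297 and 1.029. Their mean is 0.663, and 0.663 × 1.3 = 0.86 h. Multiplying by the share of sets gives the average shift.

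| Eligible records per set | Share of sets with preference | Mean shift | False-positive rate |
|---|---|---|---|
| 4 | 0% | 0 | about 5% |
| 4 | 10% | 0.10 × 0.86 = 0.09 h | about 6% |
| 4 | 25% | 0.25 × 0.86 = 0.22 h | 8-9% |
| 4 | 50% | 0.50 × 0.86 = 0.43 h | 19-20% |
| 3 | 10% | 0.05 h | just over 5% |
| 3 | 25% | 0.14 h | about 7% |
| 3 | 100% | 0.55 h | about 31% |

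The simulation gives eligible records in a set the full SD of 1.3 h. If the matching variables explain part of the spread, the shifts are smaller.

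**4. The forced-air-alone condition.** Assume control times are normal with mean 3.4 h, close to the midpoint of the plan's expected range of 45 minutes to 6 hours ((0.75 + 6)/2 = 3.375), and SD 1.3 h. Suppose some past patients still cold at a given hour were given HHBC and are therefore excluded.

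- Still cold at 4 h, 10-50% excluded: control mean falls by 0.05-0.28 h; power about 80% down to 67%.
- Still cold at 5 h, 10-50% excluded: control mean falls by 0.02-0.13 h; power about 81% down to 79%.

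Under this scenario the bias runs against HHBC. If HHBC was added for other reasons, the direction could differ.

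**The case against.** The strongest reply is that the plan does match, on four sensible variables, and that silence about the procedure is not evidence of a bad procedure. This is right as far as it goes. A reader might infer that controls will be picked by hand, that several records will fit each treated patient, or that someone will look at outcomes. The documents say none of this: they do not say whether matching is manual or programmed, or how large the pool is. Close matching could leave little choice, and with mild preference the inflation is slight.

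A reader might also infer that control status is defined over the whole stay. The text gives no time span. It may simply describe the rewarming method used, and the plan does not say that HHBC was ever added after forced air had begun. This mechanism may also oppose the first, so the two should not be added together as one false-positive concern.

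What remains is that the outcomes are already charted, the criteria stop short of fixing which records are taken, and the analysis leans entirely on that step. None of the points above closes that gap.

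**Conclusion.** The concern holds as a weakness in how controls are selected. It is not an error in the power calculation, which reproduces, nor evidence that selection will be biased. Nothing in the plan prevents knowledge of time to normothermia from influencing which 28 records are used, and nothing in the analysis would correct for it.

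The size is unknown. With four eligible records per set and no true effect, the false-positive rate runs from about 6% to 19-20% as assumed preference rises from 10% to 50% of sets. The 31% figure requires preference in every set and should not be read as a forecast. An equal shift the other way would cost power.

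The question about later HHBC is secondary. It rests on one reading of the wording, and its direction is not known. The change is one the sponsor should make because it is cheap and must be made before control outcomes are extracted.

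**What to change.** Before extracting any control outcome, write down and follow these steps:

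1. Fix a calendar window before enrolment opens and list all consecutive CTICU admissions in it that meet the same entry criteria as the prospective patients.
2. Name one baseline moment that exists in both groups, since controls have no time of heated-circuit application.
3. Extract baseline fields only: reference temperature, type of surgery, BMI and deep hypothermic arrest.
4. Choose two controls per treated patient with a pre-written matching program that states tolerances, surgery categories and tie-breaking.
5. Lock the list, then extract post-baseline temperatures.
6. Report how many records were eligible.

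For the secondary point, classify controls by the warming method at the start of rewarming. Keep any who later received HHBC with their observed time to normothermia, and report a sensitivity analysis without them. Censoring at the start of HHBC is not advised. The planned t-test or Wilcoxon test takes an uncensored time, and censoring would be informative if HHBC was added because a patient was warming slowly.

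The cost is a short program and a two-step data pull, with no extra patients and no change to the sample-size calculation. Some matches may be slightly less close. If HHBC works, keeping later recipients would dilute the contrast somewhat, and the sensitivity analysis would show by how much.

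### Matching is anchored to temperature at ANAPOD application, a moment the controls do not have, while the rest of the plan implies a clock that starts at ICU admission

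*Combined protocol and SAP*

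**What the plan says.** **Matching.** Under Exclusion Criteria, the retrospective part describes the treated group as "the 14 prospective patients who received both ANAPOD and forced warm air". The controls, two for each treated patient, are described as "28 retrospective ones who presented with hypothermia that were treated with forced warm air alone without ANAPOD". The criteria listed there include "Hypothermic Patients (Temp < 35C) undergoing cardiac surgery under CPB who received forced warm air alone", with no time of reading, and then "Temp at time of ANAPOD application would be our reference point". Type of surgery, BMI and deep hypothermic arrest complete the list.

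**Endpoint.** Purpose of the Study fixes the end of the primary endpoint at 36.5 °C or above and gives no start. Data Analysis & Statistical Considerations treats time to normothermia as a numeric outcome and mentions an origin only in a planning expectation: "It is expected that the patients will reach normothermia between 45 minutes and 6 hours after admission to the ICU". Inclusion Criteria sets prospective eligibility on admission temperature.

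**Sequence of events.** Design & Procedures has recruitment attempted on admission, with consent from next of kin or power of attorney. Then: "After consent is obtained, the clinical provider will ask the patient's nurse to place a lower body forced air warming device". The same request goes on to "ask the respiratory therapist to set up and connect a heated humidified breathing circuit".

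**Adjustment.** Data Analysis & Statistical Considerations states: "As the patients will be matched on key confounders no further adjustment is expected to be necessary".

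**The concern.** A matching rule in a historically controlled study has to be applicable to both groups. For a treated patient, temperature at application is a usable target value. For a control there is no corresponding moment, so the person abstracting charts must choose one: arrival, start of forced air, or some later reading. The plan gives no basis for that choice.

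The anchor also differs from the origin that the rest of the plan implies. A treated patient could be matched on a temperature taken after the consent delay but timed from admission. Alternatively, if the reference point is read as time zero, that patient could be timed from application while the control is timed from admission. Either way the groups would not be aligned. The primary comparison is an unadjusted t-test or Wilcoxon test, so any misalignment passes directly into the result. If time zero were chosen with the charts already open, the choice could also depend on the data.

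**Working it through.** **1. The moments set side by side**

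| Item | Treated (14) | Controls (28) |
|---|---|---|
| Eligibility temperature | On ICU admission | Below 35 °C, time not stated |
| Matching temperature | At ANAPOD application | No such moment; reading time not stated |
| Start of clock | Not defined; admission implied | Not defined; admission implied |
| Between admission and connection | Consent, then device set-up | Not applicable |

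Let d be the time from ICU admission to connection of the circuit. The written sequence implies that d is above zero, but the documents give no value.

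**2. The plan's own power figure**

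Inputs from Data Analysis & Statistical Considerations: 14 and 28 patients, SD 1.3 h, difference 1.25 h, alpha 0.05. Sidedness is not stated.

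- Standard error = 1.3 × √(1/14 + 1/28) = 0.4255 h.
- Two-sided critical value, t with 40 df = 2.021. Smallest significant difference = 2.021 × 0.4255 = 0.860 h.
- Noncentrality = 1.25 / 0.4255 = 2.94. Power from the noncentral t = 81.8%.

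This reproduces the stated 82%. A one-sided test would give 89.3%, so the plan's figure is two-sided.

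**3. What the choice of clock does**

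Let C be the mean control time, A the mean treated time from admission, and D the mean of d. Take control minus treated as the benefit.

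- Treated timed from admission: C − A.
- Treated timed from application: C − (A − D) = C − A + D.

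The two differ by exactly D, whatever the rewarming pattern. This is the gap between two clocks. Which of them is biased, and by how much, depends on how patients rewarm. Two simple cases with controls read and timed at admission show this:

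- *Remaining time depends only on current temperature.* A treated patient matched at application has the same expected remaining time, absent any effect, as the control has from admission. The application clock is then unbiased, and the admission clock carries the whole of d against the heated humidified circuit.
- *Rewarming follows time since admission, and matched patients are in effect alike at admission.* The admission clock is then unbiased, and the application clock carries the whole of d towards the heated humidified circuit.

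Background & Significance reports a sigmoid curve that is steepest 2–4 hours after admission, so elapsed time may matter as well as current temperature.

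**4. Illustration, with d assumed**

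Noncentral t with 40 df and the standard error above. Power uses a true difference of 1.25 h.

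| Assumed d | d / 1.25 h | d / 0.860 h | Power, full d against | False positives favouring the circuit, full d towards |
|---|---|---|---|---|
| 0 | 0% | 0% | 82% | 2.5% |
| 0.25 h | 20% | 29% | 63% (difference 1.00 h) | 8% |
| 0.5 h | 40% | 58% | 41% (difference 0.75 h) | 21% |

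Unrounded: power 0.818, 0.631 and 0.405; false positives 0.025, 0.083 and 0.208.

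**The case against.** The strongest reply is that the documents already point to one origin. The expected range is counted from ICU admission and directly follows the description of the primary test. Eligibility uses admission temperature, and the rewarming data in the background run from ICU admission. The reference-point line stands in a list of matching criteria, so its natural reading is a matching value and not a clock. This stands: a reader who infers that the plan offers no origin at all goes too far, as does one who infers that the investigators intend different clocks in the two groups. No section says so. The reply does not remove the problem, because treated patients would still be matched at application and timed from admission, and the control reading time would still be missing.

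A second reply is that the figures rest on an assumed delay, and that the identity in step 3 is true by definition. Both statements are correct, and the case for the change does not rest on the figures.

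It is also tempting to treat a full shift of d as a worst case. It is not one. Background & Significance describes afterdrop following bypass. If a treated patient were colder at application than at admission, the matched control would start colder and take longer, and the shift could exceed d.

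Finally, the recommended clock has a cost of its own, set out with the fix. Whether every enrolled patient stays in the analysis, given the lead-in that refers to patients who received both devices, is a separate analysis-set question and is not argued here.

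**Conclusion.** The point holds. A stated matching rule cannot be applied as written to 28 of the 42 patients, and it conflicts with the admission clock that the plan implies but does not define. Following it can misalign the groups on the primary endpoint, with no planned adjustment to correct this. It should be fixed before control data are collected.

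The omission is certain; its numerical consequence is not. The documents do not give d, so neither the size nor the direction of any bias can be stated. The power figures of 63% and 41% and the false-positive rates of 8% and 21% assume a delay of 0.25 or 0.5 h, a full shift of d, and the plan's own SD and two-sided test. They are illustrations and not bounds. A reader might infer that the design is tilted in favour of the heated humidified circuit, or that the sample-size calculation is wrong. The documents support neither: the shift can run either way or be close to zero, and the stated 82% reproduces.

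**What to change.** Before any control chart is abstracted:

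- In the retrospective part of the selection criteria, replace the ANAPOD-application line with matching on ICU admission temperature.
- Read the control temperature criterion at ICU admission, as Inclusion Criteria already does for prospective patients.
- In Data Analysis & Statistical Considerations, state that time to normothermia is counted from ICU admission in both groups.
- Record the time the heated humidified circuit was connected, and the forced-air start time in both groups, and report any difference in delay between the groups.

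**Cost.** Protocol wording and one or two charted times per patient; no change to treatment. Admission temperature is already recorded for study patients, and warming methods already go into the nursing flow sheets. Whether forced-air start can be recovered for historical controls is not stated. Time before connection will count in the heated humidified circuit group and may dilute the effect, and fewer controls may be eligible. The stated 82% power is unchanged only if the 1.25 h and 1.3 h inputs apply to the admission clock.
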